### Clinical Trials Unit

#### 1.2.4 Inclusion Criteria

- Aged 18 years or older
- 12-36 months post confirmed diagnosis of a cardiac event (myocardial infarction, angina or acute coronary syndrome)
- Able to speak and read English to participate effectively in a group education programme
- Willing and able to attend the education sessions and clinic visits
- Willing and able to give informed consent.
- Access to a mobile phone in order to receive text messages
- Willingness to allow GP notification of their participation in study and access to patient records for purpose of study
- Able to take part in moderate physical activity as assessed using Incremental Shuttle Walk Test (ISWT) (Level three or above)

#### 1.2.5 Exclusion Criteria

- Individuals with a diagnosis of heart failure where the underlying primary cause is not myocardial disease as a result of atherosclerosis will be excluded from this study
- Musculoskeletal limitations that would limit physical activity (e.g. musculoskeletal injury)
- Participation in another clinical intervention study in the past 12 weeks
- Lacks capacity to give informed consent
- Severe life-threatening co-morbidity (e.g. malignancy)
- Poor exercise capacity, (< level three on the ISWT [120 metres]), these individuals will be directed back into cardiac rehabilitation (good practice)
- Housebound or immobile
- Unstable symptoms (chest pain or breathlessness at rest; unstable stage II hypertension [160/100mmHg], not on necessary medications)
- Individuals with no or limited understanding of written or verbal English

v 1.0

Date:

20/03/2019

Clinical Trials Unit

#### 1.2.6 Sample size calculations

The primary outcome is change from baseline to 12 months average daily physical activity, as quantified by the Euclidean norm minus one (ENMO) method measured in milligravity units (mg). This is the main measure of activity derived from the activity monitor that will be used in this study (PACES). In order to detect a minimum clinically significant difference of 2.1 mg, which is equivalent to an overall increase in physical activity volume of approximately 30 minutes of light walking at 4km/h, assuming a standard deviation of 5.3 mg [1], a power of 80% and significance level of 5%, the sample size requires 202 participants. To allow for 20% loss to follow-up and 10% noncompliance of the activity monitor, we will therefore need to recruit 290 participants (145 in each group).

### 2 Outcome Measures

### 2.1 Primary outcome measures

The primary outcome measure is change in overall volume of physical activity measured using accelerometer between baseline and 12 months.

A complete case population will be used for the primary analysis. This will be followed by sensitivity analyses which will include an intention to treat (ITT) population by imputing missing data to assess the robustness of the findings to missing data.

Date:

20/03/2019

Clinical Trials Unit

### 2.2 Secondary outcome measures

Below is a list of all of the secondary outcomes collected at baseline and 12 months.

#### Aerobic fitness:

Incremental Shuttle walk test (metres) - as part of the ISWT blood pressure, heart rate, oxygen saturation, rating of perceived exertion and breathlessness will be obtained.

#### Ambulatory activity:

Patients will be asked to wear an accelerometer for up to eight days to record total physical activity, which includes light, moderate, vigorous and moderate to vigorous physical activities (MVPA). The measures will be

- Time spent above a threshold/ equivalent intensity to walking
- MVPA (1 min bouts)
- Sedentary time
- Sleep duration
- Intensity gradient metric
- Average acceleration for the most active 30 minutes per day

#### Anthropometric measures:

- Body mass (kg).
- Body mass index (kg/m²)
- Waist circumference (cm)
- Hip circumference (cm).
- Waist to hip ratio

#### Cardiovascular measures:

- Blood pressure (mmHg)
- Resting heart rate (bpm)

#### Biomedical measures:

- Total cholesterol (mmol/l)
- HDL cholesterol (mmol/l)
- LDL cholesterol (mmol/l)
- Triglycerides (mmol/l)
- HbA1c (mmol/mol, %)

#### TC:HDL ratio

- Health historyMedical history and medication
- Family history of CHD

### Smoking status, alcohol intake & employment status

SAP for study: PAP Version: v

PACES v 1.0

Date:

20/03/2019

#### Questionnaire Measures

A number of different questionnaire measures will be completed by participants at baseline, 6 months and 12 months. Details of these questionnaire measures are as follows:

- Jenkins self-efficacy for exercise expectations scale
- Hospital Anxiety and Depression scale (HADS)
- MacNew Heart Disease 7:8
- Recent Physical Activity Questionnaire RPAQ
- EuroQoL EQ-5D-5L Health-related quality of life instrument 
- Morningness- Eveningness Questionnaire 12,13 (Baseline only)

Use of health care services (12 months only) No attempt will be made to impute the missing values for the secondary endpoints measured.

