## 3 Analysis Sets/Populations

### 3.1 Missing values and outliers

[figure not shown]
Missing values represent a potential source of bias in clinical trials. Therefore, every effort will be made to ensure the data is fully explored for potential problems and have been correctly entered into the database. Participants who did not attend the baseline assessment after consent will be excluded from all analyses, but will be noted on the CONSORT flow chart. For the primary and secondary analyses, participants who do not have an outcome measurement will be excluded; as discussed in section 3.2. Sensitivity analyses will be performed to assess the robustness of the findings to missing data. Outliers will be identified by examining graphical plots such as normality plots, box plots and histograms. Values that visually appear outside of the main distribution (i.e. outliers) will be further investigated and if this is the correct observation it will remain in the analysis, however further assumptions will be made to assess possible influences on the results using a sensitivity analysis; by removing the outlier or outliers to compare results. Where results from the two analyses are discrepant, this fact will be reported and discussed in the study publication.

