## 3.2 Complete Case Population

The level of missing data for each outcome will be assessed. If missing outcome data is present the initial analysis will be based on the complete cases. All tests of the effect of treatment on outcomes will be conducted on a complete case (CC) population. That is, all

Date:

20/03/2019

the recruited participants will be included in the analysis, with the exception of those with missing outcome data. This will be done on a 'by analysis' basis, i.e. only those participants with missing data for variables required for a specific analysis will be removed.

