### 5.2 Primary Endpoint Analysis

### 5.2.1 Primary Analysis of Primary Endpoints

The primary outcome is change in overall volume of physical activity (average acceleration, ENMO) from baseline to 12 months. For the primary outcome treatment arm will be compared using linear regression modelling with

- 1. a binary indicator for randomisation group as the explanatory variable
- terms for stratification factors (gender and ethnicity) as confounders
- 3. adjustment for the change from baseline in accelerometer wear time and baseline average daily physical activity.

The primary analysis at 12 months will be based on complete data.

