### 5.3 Secondary Endpoint Analyses

The analyses of the secondary outcomes will be conducted in a similar manner as the main analysis using the appropriate model type, logistic regression for binary outcomes, linear for continuous and ordinal for ordinal outcome.

The assumptions of each analysis will be assessed and alternate parameterisations will be considered where appropriate.

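### Five questionnaires are collected at 6 months but those scores have no stated role in the analysis, so participants lost after month 6 add nothing to the 12-month comparison

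*SAP*

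**What the plan says.** - **Collection.** SAP section 2.2 opens with "Below is a list of all of the secondary outcomes collected at baseline and 12 months". Its Questionnaire Measures part gives a fuller schedule: "A number of different questionnaire measures will be completed by participants at baseline, 6 months and 12 months". The Morningness-Eveningness scale is marked baseline only and health care use 12 months only. That leaves five instruments with a 6-month wave: the self-efficacy scale, HADS, MacNew, RPAQ and EQ-5D-5L.
- **Model.** Section 5.3: "The analyses of the secondary outcomes will be conducted in a similar manner as the main analysis using the appropriate model type". The main analysis in section 5.2.1 is a linear regression of change from baseline to 12 months, and "The primary analysis at 12 months will be based on complete data".
- **Analysis set.** Section 3.2: "All tests of the effect of treatment on outcomes will be conducted on a complete case (CC) population". Section 3.1: "For the primary and secondary analyses, participants who do not have an outcome measurement will be excluded".
- **Imputation.** Section 2.2: "No attempt will be made to impute the missing values for the secondary endpoints measured". The multiple imputation in section 5.2.2.2 covers accelerometer activity only.
- **Use of month 6.** No section gives a 6-month contrast, a repeated-measures model or any other use of the 6-month scores.

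**The concern.** A participant who completes HADS at 6 months and is then lost has given the most recent information available on the missing 12-month score. Under the plan that information does not reach the 12-month comparison. A separate 6-month regression, should the analyst choose to run one, would not change this.

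Two things are at stake. The first is bias: if people leave because of how they felt at 6 months, and this works differently in the two arms, those who remain no longer give a fair 12-month contrast. Baseline adjustment does not remove it. The second is precision, which matters less. There is also a gap in specification. With no time point or role fixed for month 6, whether to analyse it, and how, can be settled after the data are seen.

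**Working it through.** **1. The plan's own figures (section 1.2.6).** Difference 2.1 mg, SD 5.3 mg, power 80%, two-sided 5%. The t-based two-sample calculation gives 100.96, so 101 per arm and 202 in total. Allowing 20% + 10% = 30%: 101 / 0.70 = 144.3, so 145 per arm and 290 in total. Both figures reproduce and are not in dispute. The SAP gives no figure for the questionnaires.

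**2. How many people are affected.** The 10% allowance is for the activity monitor, so only the 20% loss applies here.
- Lost by 12 months: 290 × 0.20 = 58. With 12-month scores: 290 − 58 = 232.
- The SAP does not give the timing of loss. Assume that 25%, 50% or 75% of it falls after month 6: 58 × 0.25 = 14.5 (about 15), 58 × 0.50 = 29, 58 × 0.75 = 43.5 (about 44).

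**3. Precision if loss is completely at random.** Using the 6-month scores lowers the variance of the 12-month contrast by about r² × (late losses / number with 6-month scores), where r is the 6/12-month correlation given baseline. If all three visits are equally correlated at ρ, then r = ρ/(1 + ρ). For assumed ρ of 0.5 and 0.7, r = 0.33 and 0.41, and r² = 0.111 and 0.170.

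| Late losses | With 6-month score | Reduction, ρ = 0.5 | Reduction, ρ = 0.7 |
|---|---|---|---|
| 15 | 247 | 0.7% | 1.0% |
| 29 | 261 | 1.2% | 1.9% |
| 44 | 276 | 1.8% | 2.7% |

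A simulation (145 per arm, 3000 replicates, effect 0.30 SD at both visits, equal correlations) gave complete-case to repeated-measures variance ratios of 1.006 to 1.031 under random loss. That agrees with the table. Neither method was biased in this setting.

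**4. Bias if late loss depends on the 6-month score.** In the same simulation, late loss in the intervention arm was made more likely for low 6-month scores, and late loss in the control arm was left random. Total loss stayed near 20%. The true effect was 0.30.

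| Share of loss after month 6 | Complete case, ρ = 0.5 / 0.7 | Using 6-month scores, ρ = 0.5 / 0.7 |
|---|---|---|
| 25% | 0.313 / 0.315 | 0.299 / 0.303 |
| 50% | 0.326 / 0.323 | 0.300 / 0.302 |
| 75% | 0.332 / 0.329 | 0.298 / 0.299 |

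The complete-case bias is 0.013 to 0.032 SD: 0.013 / 0.30 = 4% to 0.032 / 0.30 = 11% of the effect. The estimates had an empirical SD of 0.095 to 0.117, so the Monte Carlo error of each mean is at most 0.117 / √3000 = 0.002. The bias is therefore real in this set-up. It is still small beside the sampling error: 0.013 / 0.112 = 0.12 to 0.029 / 0.095 = 0.31 of a standard error.

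**The case against.** **The plan never says that the 6-month data are thrown away.** This is correct. A reader might infer that they are discarded, but section 5.3 names no time point and section 3.2 applies complete cases analysis by analysis, so a separate 6-month comparison is possible. What the text supports is narrower: no role is stated, and no reading of the plan brings participants lost after month 6 into the 12-month contrast.

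**Baseline-adjusted complete-case regression is a declared and acceptable choice for secondary outcomes.** This also stands. It is valid if loss depends only on arm and the adjusted baseline covariates. The case here is for a cheap improvement, not for an error in the planned model.

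**Loss that depends on the 6-month score need not bias the contrast.** A reader might infer that any such dependence does. If the dependence is the same in both arms and the arms do not differ at 6 months, selection acts equally and the difference is not biased. The simulation shows bias because the dependence was placed in one arm.

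**Section 3.1 promises sensitivity analyses for missing data.** It does so in general terms only. The analyses that are specified sit under the primary endpoint in section 5.2.2, and section 2.2 rules out imputation for secondary endpoints.

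**The two statements of the visit schedule do not truly conflict.** This largely stands. The five scales are collected at baseline and 12 months, as the opening line of section 2.2 says, and the Questionnaire Measures part adds month 6. The opening line needs tidying and misleads nobody about collection. A further unadjusted test at month 6 is likewise a minor matter, since section 4.1 openly makes no adjustment and separates primary from secondary outcomes.

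**Conclusion.** The point holds as a modest improvement to the secondary analysis. Five scales are measured at 6 months with no analytic role, and about 15-44 of 290 participants could have a 6-month score that never informs the 12-month comparison. That count rests on the SAP's 20% loss and on an assumed 25-75% of it falling after month 6.

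The main benefit is protection against bias when loss depends on the 6-month score and either the dependence or the scores differ by arm. In one illustrative mechanism this was 0.01-0.03 SD on a 0.30 SD effect. The precision gain is about 1-3% for equal between-visit correlations of 0.5-0.7. A reader might expect 3-6%, but with half the loss after month 6 that needs a correlation of 0.5-0.7 after baseline adjustment (0.25 × 29/261 = 2.8%; 0.49 × 29/261 = 5.4%). Equal correlations cannot give a partial value above 0.5, and the SAP gives no correlations at all.

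The primary outcome and the sample size are untouched.

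**What to change.** - For each continuous questionnaire score, fit one likelihood-based repeated-measures model to the 6- and 12-month scores. Fixed effects: arm, visit, arm-by-visit, baseline score, baseline-by-visit, gender and ethnicity. Use an unstructured covariance.
- Name the 12-month contrast as the secondary estimate and the 6-month contrast as supportive.
- Keep the planned complete-case regression as a sensitivity analysis.
- Amend the opening line of section 2.2 so that it shows the 6-month wave.

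The cost is SAP wording and one standard model per scale. No new data are needed, and the model imputes nothing, so it respects the ban in section 2.2. The limits should be stated: the result relies on data being missing at random given arm, the covariates and the 6-month score, and it does nothing for participants lost before month 6.

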## 3 Analysis Sets/Populations

### 3.1 Missing values and outliers

[figure not shown]
Missing values represent a potential source of bias in clinical trials. Therefore, every effort will be made to ensure the data is fully explored for potential problems and have been correctly entered into the database. Participants who did not attend the baseline assessment after consent will be excluded from all analyses, but will be noted on the CONSORT flow chart. For the primary and secondary analyses, participants who do not have an outcome measurement will be excluded; as discussed in section 3.2. Sensitivity analyses will be performed to assess the robustness of the findings to missing data. Outliers will be identified by examining graphical plots such as normality plots, box plots and histograms. Values that visually appear outside of the main distribution (i.e. outliers) will be further investigated and if this is the correct observation it will remain in the analysis, however further assumptions will be made to assess possible influences on the results using a sensitivity analysis; by removing the outlier or outliers to compare results. Where results from the two analyses are discrepant, this fact will be reported and discussed in the study publication.

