#### Clinical Trials Unit

#### 1.2.2 Randomisation

Participants will be randomised 1:1; stratified by gender (male; female) and ethnicity (White European; other) to either intervention or control groups.

If two people are taking part from the same household they will be randomised to the same arm to prevent contamination taking place.

Control participants will be sent a standard information booklet and letter informing them of their results and the outcome of randomisation. Intervention participants will also be sent a letter informing them of their results and the outcome of randomisation and subsequently contacted to book them onto an education programme.

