# 4 General Issues for Statistical Analysis

# 4.1 Multiplicity, Multiple Comparisons and Interim Analyses

All tests and reported p-values will be two-sided, where a p-value of < 0.05 will be considered to be statistically significant. Estimates will be presented with 95% confidence intervals. There will be no formal adjustment for multiple significance testing. The outcomes however, are clearly categorised by the degree of importance (primary and secondary). No formal interim analyses were planned.

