#### 5.2.2.2 Intention-to-treat Population

To allow for full analysis set, missing data will be imputed using a multiple imputation procedure which substitutes predicted values from a regression equation. The imputation will be carried out by the MI command in Stata 15. MI replaces missing values with multiple sets of simulated values to complete the data, performs standard analysis on each completed dataset, and adjusts the obtained parameter estimates for missing-data uncertainty using Rubin's rules to combine estimates 16.

The following procedure will be followed:

- The MI will be set as wide
- The MI will register imputation of the average daily physical activity at 12 months and at baseline

Date:

20/03/2019

Clinical Trials Unit

A regression method will be used, where the registered variables will be individually
adjusted for the randomisation and stratification factors (sex and ethnicity), with 100
imputations to avoid biased estimates, rseed (2259) and the force options

 MI estimate will provide the final results using the same regression model as the primary analysis and covariate adjustments.

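### No planned missing-data analysis departs from missing at random, so neither agreement nor disagreement with the complete-case result would show robustness

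*SAP*

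**What the plan says.** The primary analysis is a complete-case linear regression of change in ENMO (SAP 2.1, 3.2, 5.2.1). Its covariates are arm, gender, ethnicity, baseline activity and change in accelerometer wear time.

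Section 3.1 names missing values as a possible source of bias and promises: "Sensitivity analyses will be performed to assess the robustness of the findings to missing data". Section 2.1 says how: an ITT population is formed "by imputing missing data to assess the robustness of the findings to missing data".

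The analyses that follow are:

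- **Imputation (5.2.2.2).** Only ENMO at baseline and at 12 months is registered for imputation. These variables are "adjusted for the randomisation and stratification factors (sex and ethnicity), with 100" imputations. The primary model is then fitted and the results are combined by Rubin's rules.
- **Per protocol (3.4, 5.2.2.1).** Intervention participants must have attended at least one session, and both arms need complete outcomes.
- **Interactions (5.2.2.3) and outlier removal (3.1).** Neither concerns missingness.

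Section 1.2.6 plans for substantial loss: "To allow for 20% loss to follow-up and 10% noncompliance of the activity monitor", the target is raised from 202 to 290. The SAP does not name its missing-data assumption. Missing at random follows from the method.

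**The concern.** A sensitivity analysis for missing data is informative when it changes the assumption on which the main analysis rests. Here that assumption is that, given the variables in the model, participants without a 12-month recording resemble those with one. The imputation keeps an assumption of this kind. It draws missing values from a regression fitted to observed participants, without any shift.

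Participants know their allocation (1.2.2 describes a letter telling them), and the intervention asks them to be more active. It is plausible that some who disengage are also less active and do not return a valid recording. In that event both analyses can overstate the effect, and their agreement could be reported as robustness when nothing has been tested. With up to three in ten primary outcomes expected to be missing, the part of the result that rests on this assumption is not small.

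**Working it through.** **Inputs from the SAP.** Section 1.2.6: "In order to detect a minimum clinically significant difference of 2.1 mg", with SD 5.3 mg; "a power of 80% and significance level of 5%, the sample size requires 202 participants". Section 4.1: "All tests and reported p-values will be two-sided". Allocation is 1:1 (1.2.2).

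**1. Reproduce the plan's figures.** A two-sided 5% t-test with difference 2.1, SD 5.3 and 80% power needs 101 per arm, 202 in all (power 80.0%), which matches. For the allowance, 202 / (1 - 0.30) = 288.6, close to 290. Applied in sequence, 202 / (0.80 x 0.90) = 280.6. The implied missing share is therefore 30% if the losses are added, or 1 - 0.72 = 28% if they are sequential.

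**2. Precision at the planning values.** SE = 5.3 x sqrt(2/101) = 0.746 mg. At an observed difference of 2.1 mg, z = 2.1 / 0.746 = 2.82 and the lower 95% limit is 2.1 - 1.96 x 0.746 = 0.64 mg.

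**3. Effect of a departure from missing at random.** Suppose missing intervention participants do worse than predicted by delta, missing controls are not shifted, and the SE is unchanged. The ITT difference falls by (missing share) x delta. Significance is lost at delta = 0.638 / share, and the difference reaches zero at delta = 2.1 / share.

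| Missing share | Significance lost at | Difference zero at |
|---|---|---|
| 20% | 3.2 mg | 10.5 mg |
| 28% | 2.3 mg | 7.5 mg |
| 30% | 2.1 mg | 7.0 mg |

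If delta is 2.1 mg, the difference is 2.1 x 0.72 = 1.51 mg (28%) or 2.1 x 0.70 = 1.47 mg (30%), with z about 2.03 or 1.97.

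**4. What the planned analyses would show.** This was simulated with 290 participants, about 30% missing per arm, residual SD 5.3, true effect zero, 600 runs and 20 imputations. Assumed, not from the SAP: baseline SD 8, slope of change on baseline -0.2, and a logistic missingness model in the intervention arm. Wear time was not modelled. Entries are mean bias in mg, with the false-positive rate in brackets.

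| Who is missing in the intervention arm | Complete case | Imputation as written | Imputation with baseline added |
|---|---|---|---|
| Those with low change (not at random) | +1.36 (45%) | +0.88 (10%) | +1.36 (44%) |
| Depends on baseline activity only (at random) | -0.01 (5%) | +1.56 (30%) | -0.01 (5.5%) |

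In the first row every unshifted analysis is biased. Shifting the imputed intervention values by -4 or -5 mg, with baseline in the imputation, gave +0.09 or -0.14 mg. In the second row the planned imputation departs from a correct primary result only because it leaves out baseline activity.

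**5. Wear time.** Section 5.2.1 adjusts for change in wear time, but 5.2.2.2 does not register wear time for imputation and then fits the same model. A participant with no 12-month accelerometer record would probably have no wear-time change, and so would drop out of the imputed analysis again.

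**The case against.** The strongest objection is that the two analyses do not make the same assumption. The primary model conditions on baseline activity and wear-time change and the imputation does not, so they can give different answers. This stands. A reader might infer that the imputation must reproduce the complete-case result, but the SAP does not support that. With 28% missing and intervention leavers shifted by a constant 2.1 mg (true difference 1.51), complete case gave 2.13 and the planned imputation 2.12-2.13. When intervention-arm missingness depended on baseline (true difference 2.1), they gave 2.07 and 3.20. The divergence comes from a thinner imputation model, though, and is not a test of missing not at random.

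The size is also open to challenge. The table in step 3 assumes that all missing intervention participants shift and no missing controls do. Part of the allowance is for not wearing the monitor, which need not mean disengagement. If only the 20% lost to follow-up lost the whole 2.1 mg, the difference would be 2.1 x 0.80 = 1.68 mg and z about 2.25. The SAP gives no pattern of dropout. This stands too, so the figures are illustrations.

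Finally, the SAP does not claim to test missing not at random, section 2.1 does not present imputation as the only sensitivity analysis, and the per-protocol set serves another purpose. All true, but no other missing-data analysis is specified, and the purpose stated in 3.1 and 2.1 is robustness.

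**Conclusion.** The point holds. None of the specified analyses varies the missing-data mechanism, so the stated purpose of assessing robustness to missing data is not met. Agreement between the primary and imputed analyses would not establish robustness, and disagreement could simply reflect the omission of baseline activity and the handling of wear time.

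At the planning values, a shift of about 2.1-2.3 mg in missing intervention participants would decide significance. This rests on 28-30% missing, unshifted controls, an observed difference equal to the planned 2.1 mg and an SE of 0.746 mg. With 20% missing the figure is 3.2 mg.

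A reader might go further and infer that the primary estimate is biased or invalid. The SAP does not support that, since it holds no information on who will be missing. What lacks support is the robustness claim. The change should be made, but the primary analysis does not fall without it.

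**What to change.** In SAP 5.2.2.2:

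1. Put the primary model's covariates, baseline activity and wear time, in the imputation model. Impute missing 12-month wear time, or state how else it is handled, so that imputed participants stay in the analysis. This has to come first. A shift applied to the present imputation would inherit its error when missingness depends on baseline, and would do nothing for participants who then drop out for want of wear time.
2. On those datasets, prespecify a delta-adjusted analysis. Shift imputed 12-month ENMO unfavourably in the intervention arm, then in both arms, over a stated grid (for example 0 to 4.2 mg, twice the planned difference). Combine by Rubin's rules and report the shift at which the conclusion changes.
3. Label the unshifted imputation as a missing-at-random analysis, and align the wording of 2.1 and 3.1 with this.

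The cost is SAP text and a modest amount of extra code, with no new data. The SAP's introduction allows amendment before database lock. The downside is a little more analysis work and a conclusion that may look less secure.
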